11.7.1 Missing Data

Although quite unlikely, mechanisms for handling missingness in our response data will be appropriate to the underlying analytic strategy²⁶⁹ but tempered by available sample size. In linear and nonlinear mixed models likelihood-based inference using only the non-missing responses is valid under the MAR, i.e., missingness is dependent only on the observed data. The alternative missingness mechanism--missing completely at random (MCAR) assumes missingness does not depend the responses, observed or not. Other approaches such as inverse-probability weighting^{270,271} will be investigated to accommodate missing data patterns that are neither MCAR or MAR^{272,273} an approach that we used in analyzing longitudinal censored medical costs data.^{274,275}

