2.1.13 Hypothesis

Description of the Study Refining the standard clinical case definition of CM to include malarial retinopathy may improve specificity and focusing on retinopathy-positive CM participants with moderately severe increased brain volume identifies the group at highest risk of dying.

Our data suggest that these children experience a disruption of the respiratory control center manifesting as a respiratory arrest. The final cause of death appears to be respiratory arrest secondary to intracranial hypertension.

Hypothesis: Death in children with CM occurs when raised intracranial pressure from severely increased brain volume impairs the function of the medullary respiratory center; interventions which reduce brain volume or support ventilation will improve survival rates in CM patients.

Using numbers derived from the ongoing studies in Malawi, of 100 children who meet the standard clinical case definition of CM, approximately 70-75 will be retinopathy-positive. Of these, ~ 47% (34-35 children) will have severely increased brain volume on MRI, and, with the observed mortality rate of 37% in this clinical subset, about 12 of these children will die. The majority recover quickly and completely, suggesting that the adverse effects of increased brain volume on respiratory status are reversible and short-lived⁵².

All CM patients enrolled in the study will contribute to the evaluation of surrogate markers of brain volume.

CM patients who are retinopathy-negative and who have evidence of increased brain volume on MRI will be eligible to be enrolled in an identical interventional study (of assisted ventilation or hypertonic saline). This group, when combined with the retinopathy-positive CM patients described above, represents children who satisfy the less stringent but standard WHO definition of cerebral malaria⁸¹. In order to increase generalizability of our study results, we will analyze data from this combined group, but perform a sensitivity analysis to determine if treatment effects vary in children of different retinopathy status.

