For assessments made serially over time, the outcome is a vector $\mathbf{Y}_i = (Y_{i1}, Y_{i2}, \dots, Y_{im})'$ of repeated continuous (e.g., sheath diameter on admission and then twice daily) or repeated binary indicators (e.g., severe neurologic sequelae at 1, 6 and 12 months). Generalized linear models $g(E(Y_{ij} | \mathbf{x}_i)) = \mathbf{x}'_j \beta + \mathbf{z}'_j \mathbf{b}_i$ are apropos with right hand side covariates specific to the j -th time, \mathbf{z}_j will include an intercept and terms involving time permitting assessment of the evolution of the mean outcome (or probability for binary outcomes) over time, both within-subject and across the study population (i.e., population average). The link g is the identity function for continuous responses, and the logit for binary responses. Correlations between components of \mathbf{Y}_i are incorporated via the random effects. A judicious choice of covariance structure for \mathbf{b}_i will be elicited from information criteria.²⁶³⁻²⁶⁵ Alternating logistic regression will be considered the case of binary responses.²⁶⁶ Repeated ordinal measures (e.g., brain volume) will be analyzed by proportional odds or partial proportional odds models.^{267,268}

In all analytic procedures we will examine the overall goodness-of-fit, and presence of influential and/or outlying data points with graphical techniques and formal residual analyses.

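### Inverse-probability weighting is assigned to data that are not missing at random, but as specified it relies on missing at random

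*Combined protocol and SAP*

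**What the plan says.** Section 11.7.1 of the Combined protocol and SAP sets out three things in order.

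- On its mixed models, whether linear or not, the plan's position is this: "likelihood-based inference using only the non-missing responses is valid under the MAR, i.e., missingness is dependent only on the observed data".
- The alternative mechanism it names is this: "missing completely at random (MCAR) assumes missingness does not depend the responses, observed or not".
- For everything else, "Other approaches such as inverse-probability weighting" are named, and these "will be investigated to accommodate missing data patterns that are neither MCAR or MAR". The authors add that this is "an approach that we used in analyzing longitudinal censored medical costs data".

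The section gives no expected rate of missing data and opens by treating the problem as remote: "Although quite unlikely, mechanisms for handling missingness in our response data will be appropriate to the underlying analytic strategy". It states no weight model, no selection model for the unobserved response, and no sensitivity parameter. The one sensitivity analysis named in the document, in section 2.1.13, has a different purpose: to "perform a sensitivity analysis to determine if treatment effects vary in children of different retinopathy status".

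The repeated outcome most open to loss is named in section 11.7: "severe neurologic sequelae at 1, 6 and 12 months". That section would model it with random effects, and it also says alternating logistic regression will be considered for binary responses.

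**The concern.** Once MCAR and MAR are excluded, what remains is missingness that depends on values nobody recorded. Ordinary inverse-probability weighting estimates each child's chance of being observed from recorded variables and weights by its inverse. That removes bias when the recorded variables explain the missingness. It cannot remove bias from unrecorded outcomes, because they do not enter the weights. The method therefore does not match the task it is given.

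What is at stake is the comparison of neurological outcomes among survivors, the first secondary objective in section 3.1. Section 2.3 itself warns that ventilatory support may leave some survivors with severe sequelae, so the safety reading of this trial depends partly on these data. Section 5.3.4 foresees children withdrawing before the 12-month visit. For withdrawn children, sections 5.3.4 and 7.5 arrange or request a return at 28 days or 1 month only. Some missing 6- and 12-month outcomes are therefore foreseeable, although section 11.7.1 calls missing responses unlikely.

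**Working it through.** The plan gives no figure on this point, so there is nothing of its own to reproduce. Two checks follow.

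**Check 1: what standard weighting can remove.** This is an exact expectation with assumed inputs, none from the documents. X is a binary baseline variable that is always observed, Y is a binary outcome, and R = 1 means Y is observed. P(X=1) = 0.5, P(Y=1|X=0) = 0.10 and P(Y=1|X=1) = 0.40, so the true rate is 0.5 × 0.10 + 0.5 × 0.40 = 25.0%. The weights are 1/P(R=1|X), the only ones estimable here. The weighted estimate is then the average over X of P(Y=1|X, R=1).

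- *MAR:* 90% observed if X=0, 60% if X=1. Complete cases: (0.9 × 0.10 + 0.6 × 0.40)/(0.9 + 0.6) = 0.33/1.5 = 22.0%. Weighted: 0.5 × 0.10 + 0.5 × 0.40 = 25.0%. The bias is removed.
- *MNAR, mild:* 90% observed if Y=0, 80% if Y=1 (12.5% missing overall). For X=0: 0.08/(0.08 + 0.81) = 8.99%. For X=1: 0.32/(0.32 + 0.54) = 37.21%. Weighted mean 23.1%; complete cases 22.9%.
- *MNAR, stronger:* 90% observed if Y=0, 50% if Y=1 (20% missing overall). For X=0: 0.05/(0.05 + 0.81) = 5.81%. For X=1: 0.20/(0.20 + 0.54) = 27.03%. Weighted mean 16.4%; complete cases 15.6%.

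The full set under MNAR is:

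| Observed if Y=1 | Missing overall | Complete cases | Weighted | Weighted bias (points) |
|---|---|---|---|---|
| 80% | 12.5% | 22.9% | 23.1% | −1.9 |
| 70% | 15.0% | 20.6% | 21.1% | −3.9 |
| 60% | 17.5% | 18.2% | 18.8% | −6.2 |
| 50% | 20.0% | 15.6% | 16.4% | −8.6 |

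Weighting removes about 11% of the complete-case bias in the first row ((2.14 − 1.90)/2.14) and about 8% in the last ((9.38 − 8.58)/9.38). This shows how the method behaves. It does not forecast this trial.

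**Check 2: how far missing outcomes could move a rate here.**

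- Arm size 32: projected total for VENT and for HPS, section 4.
- Mortality 18%: the rate VENT is powered to detect in section 11.5, used here as an assumption.
- Survivors: 32 × 0.82 = 26.2, about 26.
- Missing: 3 to 5 children, assumed, because the plan gives no rate.
- Best-to-worst range = missing/survivors: 3/26 = 11.5% and 5/26 = 19.2%, so about 12 to 19 percentage points.

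This is the distance between all missing children having sequelae and none having them. It exists whatever method is used.

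**The case against.** The strongest reply has four parts, and much of it stands.

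**The plan commits to little.** Weighting is one example of a class of approaches to be looked into, and the stated main approach, likelihood inference under MAR, is described correctly. That is right. A reader might infer that the plan offers weighting as its sensitivity analysis and so would give false reassurance. Section 11.7.1 never uses that label, so the documents do not support this reading.

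**Weighting is not inherently limited to MAR.** It can be extended with an explicit non-ignorable selection model or a fixed sensitivity parameter. That is also right, and it rules out saying that weighting can never serve under MNAR. It does not rescue the text, which supplies neither. The cited sources could not be consulted, so the point concerns what the plan itself specifies.

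**Disability-related loss need not be MNAR.** A reader might infer that any loss at 6 or 12 months linked to disability is non-ignorable. Sections 3.2.2 and 7.3 place an assessment at 1 month. If the recorded 1-month status drives later loss, the mechanism is MAR on the plan's definition, and a mixed model using all three visits already covers it. What remains is loss before the 1-month visit, or loss driven by later change that was not recorded.

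**The figures do not measure harm to this trial.** This is accepted. The 12 to 19 points is the assumed missing fraction, and the illustration rests on assumed probabilities.

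The authors may have meant weighting to relax MCAR to MAR for an estimating-equation analysis such as the alternating logistic regression in section 11.7. That would be a sound use, but the sentence would still name the wrong mechanism.

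**Conclusion.** The point holds as a limited one: section 11.7.1 is wrong as written. It assigns a method that, in standard form, needs MAR to data it has defined as not MAR, and it specifies nothing that would extend the method. The document contains no analysis addressing MNAR for the follow-up outcomes.

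The consequence is confined to secondary outcomes, chiefly sequelae at the three follow-up visits. The primary outcome is determined within 7 days, mostly in hospital, and is little exposed. The size of any bias cannot be stated, because it depends on a missing rate and a mechanism that the documents do not give. The only trial-scaled figure available is the bound from the second check, which rests on 18% mortality and 3 to 5 missing children in an arm of 32. Severity is low: this is a correction worth making, and it does not threaten the trial's main conclusion.

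**What to change.** 1. Reword section 11.7.1 so that inverse-probability weighting is described as a method under MAR, for example for the alternating logistic regression. Name the variables in the weight model, including outcome status at earlier visits.
2. For MNAR, prespecify a tipping-point table by arm for sequelae at 1, 6 and 12 months. Move missing outcomes from no sequelae to sequelae, separately in each arm, until the conclusion changes, and report the best and worst cases. A delta-adjusted analysis would serve equally well.
3. Report the number of survivors with missing outcomes by arm and visit, so that the range can be read against actual loss.

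The cost is a few sentences and one extra table. Trial conduct, sample size and the primary analysis do not change.

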11.7.2 Additional exploratory modeling

Since Arm 2 (HPS) and Arm 3 (UC) are likely to have an intermediate endogenous binary outcome Y_{i1} of treatment success prior to final outcome of survival Y_{i2} , we will consider joint modeling for (Y_{i1}, Y_{i2}) via a two-part specification: (1) conditional model for $P[Y_{i2} = 1 | Y_{i1} = 1, \mathbf{x}_i]$ -- i.e., probability of survival given treatment success and (2) $P[Y_{i1} = 1 | \mathbf{x}_i]$ --i.e., the probability of treatment success. Both two-stage and full likelihood-based estimation of the joint model are feasible.^{270,276}

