Description of Agent or Intervention:	
Arm 1: Usual care + immediate ventilatory support for a maximum of 7 days. Brain death or death will be considered a failure of the primary intervention.
 
Arm 2: Usual care + infusion of 3% hypertonic saline to achieve a blood sodium concentration of 150-160 mmol/L. Ventilatory support will be provided to patients who experience a respiratory arrest, and this will be considered a failure of the primary intervention.
 
Arm 3: Usual care (elevation of the head of the bed 30 degrees and intravenous antimalarial drugs). Ventilatory support will be provided to patients who experience a respiratory arrest, and this will be considered a failure of the primary intervention.
 
Final outcomes will be determined at 7 days post-randomization: The primary study outcome will be recovery vs treatment failure, where treatment failure is a composite of death, ventilatory rescue (Arms 2 and 3), and brain death

Objectives:

Primary Objective

Compare final outcomes in pediatric CM patients receiving usual care (Arm 3) with both of two interventions (Arm 1 and Arm 2).

Secondary Objectives:

[figure not shown]
1. Among survivors of this interventional study, compare rates of adverse neurological outcomes in those assigned to the two interventions and those assigned to usual care.
2. Among all children admitted to the Paediatric Research Ward and screened for eligibility for randomization, evaluate and validate biomarkers of increased brain volume.
3. Assess the safety of early mechanical ventilation as well as intravenous hypertonic saline in children with CM.
4. Establish association between specific pathogenic mechanisms and TCD-derived phenotypes.

Description of Study Design:

Prospective, randomized, controlled non-blinded clinical trial

Estimated Time to Complete Enrollment:

Six years

PICU¹: will be on continuous monitoring 24hrs, then transferred to PRW

²pts in Arms 2 and 3 who experience respiratory arrest will be placed on ventilators.

³Treatment failure is a composite of death, ventilatory rescue or brain death

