3.2 Study Outcome Measures

3.2.1 Primary Outcome Measures

Final outcomes will be determined within 7 days: treatment success or failure, where failure is a composite outcome of death, ventilatory rescue, and brain death. Final outcomes within 7 days in children who meet the standard WHO definition of cerebral malaria treatment success or failure, where failure is a composite outcome of death, ventilatory rescue, and brain death.

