1. Arm 1: Usual care + immediate mechanical ventilatory support (VENT) for a maximum of 7 days, with ventilator withdrawal once brain volume has decreased (brain volume score ≤ 5) or the patient has improved clinically (modified Blantyre Coma Score ≥ 3) or the patient dies or meets criteria for severe irreversible neurologic failure.
2. Arm 2: Usual care + intravenous hypertonic saline (HPS) for a maximum of 7 days, withdrawn once brain volume has decreased (brain volume score ≤ 5) and the patient

has improved clinically (Blantyre Coma Score ≥ 3) or the patient dies or meets criteria for severe irreversible neurologic failure.

3. Arm 3: Usual care (UC); intravenous fluids, intravenous artesunate; antipyretics, anticonvulsants and blood transfusions as needed; nutritional support) for a maximum of 7 days, or until brain volume has decreased (brain volume score ≤ 5) and the patient has improved clinically (Blantyre Coma Score ≥ 3) or the patient dies or meets criteria for severe irreversible neurologic failures

Participants will remain in the study throughout their hospitalization and, in survivors, through the 12-month post-randomization follow-up visit. Children are discharged when two sequential 6-hourly blood films are free of malaria parasites, when they have been afebrile for 24 consecutive hours, and when they are able to take medications and food by mouth. Final data collection will be at 12 months post-randomization.

Stratification:

No stratification is required. The ages of retinopathy-positive CM with severely increased brain volume per MRI who survived were compared to those of participants from the same population that died. There was no difference in the age structure (data not shown, $p=0.95$).

Primary and secondary outcomes.

The primary outcome is treatment success or failure, determined within the first 7 days. Treatment success is recovery. Treatment failure is death, ventilatory rescue (for participants in Arms 2 and 3) or meeting criteria for severe irreversible neurologic failure.

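### The exploratory joint model in Section 11.7.2 leaves out survival among children with Y1 = 0, and under the protocol's own definition of success its conditional part is fixed at 1

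*Combined protocol and SAP*

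**What the plan says.** Section 11.7.2 concerns Arms 2 (HPS) and 3 (UC). It treats success of the allocated treatment, Y1, as an "intermediate endogenous binary outcome" that precedes survival, Y2. It proposes to model the pair in two parts:

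1. P[Y2 = 1 | Y1 = 1, x], described as the "probability of survival given treatment success";
2. P[Y1 = 1 | x], described as "the probability of treatment success".

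It adds that two-stage and full-likelihood estimation are both feasible. It gives no model for P[Y2 = 1 | Y1 = 0, x], no definition of Y1 and no time horizon for Y2.

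Success and failure are defined elsewhere:

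- Section 4 (primary and secondary outcomes): "Treatment failure is death, ventilatory rescue (for participants in Arms 2 and 3) or meeting criteria for severe irreversible neurologic failure". Success is recovery.
- Protocol Summary: "treatment failure is a composite of death, ventilatory rescue (Arms 2 and 3), and brain death". For Arms 2 and 3 it says of rescue: "Ventilatory support will be provided to patients who experience a respiratory arrest, and this will be considered a failure of the primary intervention".
- Section 3.2.1: "where failure is a composite outcome of death, ventilatory rescue, and brain death".
- Section 2.3 likewise classes children in Arms 2 and 3 who are rescued, die or are brain dead as failures.

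The Protocol Summary and Sections 3.2.1, 4 and 11.4 all place the final outcome at or within 7 days.

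**The concern.** If Y1 is the protocol's treatment success, it already contains survival to day 7. Conditioning on it leaves nothing to model in part (1). The children in whom survival is uncertain are those with Y1 = 0, and the plan writes no model for them.

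Rescue counts as failure in Arms 2 and 3 but not in Arm 1, so a reader of the composite will want to know how many failures were rescues and how many rescued children lived. Section 11.7.2 is where the plan sets out to model success and survival jointly. As written it either repeats the primary composite or gives an incomplete model, and neither answers that question.

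**Working it through.** The plan states no figure for this analysis, so there is none to reproduce. The check has four steps.

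**1. Possible 7-day states in Arms 2 and 3, with Y1 as the protocol's composite**

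| State at day 7 | Y1 (success) | Y2 (survival) |
|---|---|---|
| Recovered, never rescued | 1 | 1 |
| Rescued, alive | 0 | 1 |
| Rescued, died | 0 | 0 |
| Died without rescue | 0 | 0 |
| Brain death | 0 | 0 |

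Given Y1 = 1, the only possible value of Y2 is 1. Given Y1 = 0, both values occur, and only rescued children can supply Y2 = 1. Scoring brain death as not surviving is an assumption. It does not affect the Y1 = 1 row.

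**2. What a logistic fit of part (1) does.** Take 64 UC children (the minimum in Section 11.7) and 36% failure (the UC mortality in Sections 4 and 11.5, used as a stand-in). The number of successes is 64 × 0.64 = 41, all with Y2 = 1. The log-likelihood at intercept b is −41 × log(1 + e^−b):

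| b | Log-likelihood |
|---|---|
| 2 | −5.20 |
| 5 | −0.28 |
| 10 | −0.0019 |
| 20 | about 0 |

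It rises without reaching a maximum, so no finite estimate exists. What remains is P[Y1 = 1 | x], the primary composite restricted to two arms.

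**3. Identification under any definition.** Two binary variables have three free probabilities per covariate pattern, and the plan specifies two. By the law of total probability,

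P(Y2=1) = P(Y1=1) × P(Y2=1 | Y1=1) + P(Y1=0) × P(Y2=1 | Y1=0).

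The last factor, q, is missing and can lie anywhere from 0 to 1. The two parts therefore leave overall survival open over an interval of width P(Y1=0).

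Under the composite definition, with failure rate f, survival is (1 − f) + f × q. The documents give no q and no failure rate. The two UC mortality figures, 36% (Sections 4 and 11.5) and 28% (Section 11.6), stand in for f:

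| f | q = 0 | q = 0.25 | q = 0.5 | q = 0.75 | q = 1 |
|---|---|---|---|---|---|
| 0.36 | 0.64 | 0.73 | 0.82 | 0.91 | 1.00 |
| 0.28 | 0.72 | 0.79 | 0.86 | 0.93 | 1.00 |

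If Y1 = 1 means no rescue, a child can die unrescued and part (1) can vary. Survival is then P(no rescue) × P(survive | no rescue) + P(rescue) × P(survive | rescue). The plan supplies the first product and P(rescue), but not the last factor.

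**4. How much data the missing term would have.** The projected enrolment table in Section 4 gives 68 UC children. Removing the 48 historical controls leaves 20 randomised. Adding 32 HPS children gives 52. With the same stand-ins, failures number 52 × 0.28 = 14.6 to 52 × 0.36 = 18.7, about 15 to 19 over both arms. If all 64 UC children were kept at 36%, the counts would be 64 × 0.36 = 23 in UC and 32 × 0.36 = 12 in HPS. The rescued children are some unstated fraction of these failures.

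**The case against.** The best reply is that Section 11.7.2 need not mean the full composite. It calls Y1 intermediate and distinct from the final outcome. Section 11.4 describes failure in Arms 2 and 3 as the allocated treatment failing so that rescue ventilation is needed. Read that way, a child can die without rescue and part (1) takes both values. This stands: a reader might infer that part (1) must always be constant, and the documents support that only under the composite definition. It does not rescue the specification, because survival among children with Y1 = 0 is missing on this reading too. The same holds if Y2 means survival beyond day 7.

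Four other inferences are tempting and not supported:

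- *That the plan cannot compare survival by arm.* Section 9.1 makes survival in the three arms the primary safety parameter, Sections 11.6 and 11.7 frame the VENT test on mortality, and Section 11.6 reports HPS deaths separately.
- *That later survival given success is near 1.* The figure in Section 2.3, 85% by 72 hours, pools deaths with discharges and says nothing about survival after day 7.
- *That for the historical controls Y1 and Y2 are the same event.* That depends on the definition of Y1, and Section 11.7.2 does not say whether they enter this model.
- *That modelling survival among all failures would be enough.* Pooling rescued children with unrescued deaths, whose Y2 is 0 by definition, mixes how often rescue happened with how well it worked.

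Finally, the section is headed as exploratory and commits only to considering the model. That is correct and sets the severity.

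**Conclusion.** The specification is wrong as written, at minor severity. Under the protocol's definition of failure, part (1) equals 1, cannot be estimated by logistic regression, and the model reduces to the primary composite. Under the no-rescue reading, part (1) is estimable but the model is incomplete. Under neither reading do the two parts identify the joint distribution of success and survival.

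The gap in overall survival equals P(Y1 = 0): 0.36 or 0.28 if UC mortality stands in for the failure rate. These are ranges from an assumption and not estimates, since failure also includes rescued survivors and the documents state no failure or rescue rate. The figure of 15 to 19 failures rests on the same stand-ins and on projected enrolment. The non-identification result rests on no numerical assumption.

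The primary test, its boundaries, the sample size and the Section 9.1 survival comparison do not depend on this model.

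**What to change.** Rewrite Section 11.7.2 as follows.

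- Define the intermediate variable as rescue ventilation (yes/no), separate from the composite. State the time horizon of Y2 and how brain death is scored.
- For randomised HPS and UC children, report by arm, as counts with exact confidence intervals: (a) the proportion rescued; (b) survival among rescued children; (c) survival among children not rescued.
- Obtain overall survival as P(no rescue) × P(survive | no rescue) + P(rescue) × P(survive | rescue).
- If a joint model is kept, add the component for survival given rescue and limit covariates, given the few failures expected.
- Leave the 2014–2017 historical controls out of this analysis. Section 2.3 dates mechanical ventilation in the unit from July 2017, and Section 4 describes the unit as still under construction in 2017. Rescue was therefore essentially unavailable to these children, and they cannot inform survival after it.

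The cost is a few lines of text. No new data are needed, because rescue and death are already components of the primary outcome in these arms.
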